4.2 Handling of Dropouts

All data available will be analyzed.

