4.3 Handling of Missing Data

All missing or partial data will be presented in the subject data listing as they are recorded on the Case Report Form (CRF).

The number of subjects who prematurely discontinue the study and study treatment for any reason, as well as the reasons for premature discontinuation of study and study treatment, will be reported.

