4.5 Data Rules

In general all analyses will be performed for the safety set. It is anticipated that the analysis sets will not differ. Otherwise valuable data which is not available in the safety set will also be analysed. See section 5 for definition of the analysis sets.

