6.6 Safety

All analyses will be conducted in the safety set.

AEs will be coded using the latest version of MedDRA during the study. A treatment-emergent adverse event (TEAE) is defined as an AE that increase in severity or that is newly developed after the first study intervention.

If the onset date of an AE is missing/incomplete, it is assumed to have occurred after the first study intervention (i.e., a TEAE) except if the partial onset date or stop date indicates differently.

An overview over all patients experiencing AEs will be given. The total number of patients experiencing TEAEs will be presented and tabulated by SOC and PT and CTCAE grade.

The following categories will be presented:

- TEAEs
- Drug-related TEAEs
- TEAEs leading to discontinuation of study drug
- Treatment-emergent serious adverse events (TESAEs)
- Drug-related TESAEs
- TESAEs leading to discontinuation of study drug

All deaths, TESAEs, TEAEs leading to discontinuation and pregnancies will be presented in subject listings, if applicable.

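### SAP 6.6 names no specific grade output, non-fatal SAE listing or discontinuation category for reportable events that neither start nor worsen after the first rollover dose (minor)

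*SAP*

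**What the plan says.** Protocol section 3 pairs the documentation of safety, a primary objective, with an endpoint on the frequency and the severity of SAEs and protocol-specified AEs. Protocol 9.4.2 plans descriptive frequency tables of those observed in the study and leaves details to the SAP. The Schedule of Activities (protocol 1.3) and protocol 8.3.1 define what is recorded. This includes ongoing as well as new SAEs, ongoing Grade 3/4 or vital-organ Grade 2 events re-graded to CTCAE v5.0, and events that begin or deteriorate after consent, even if before the first dose.

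SAP 6.6 works from a treatment-emergent definition: "A treatment-emergent adverse event (TEAE) is defined as an AE that increase in severity or that is newly developed after the first study intervention". The grade output follows it: "The total number of patients experiencing TEAEs will be presented and tabulated by SOC and PT and CTCAE grade". On listings it says: "All deaths, TESAEs, TEAEs leading to discontinuation and pregnancies will be presented in subject listings, if applicable". One sentence is not filtered, but its content is not described: "An overview over all patients experiencing AEs will be given". A default for undated events widens the treatment-emergent group: "If the onset date of an AE is missing/incomplete, it is assumed to have occurred after the first study intervention", unless a partial onset date or the stop date shows otherwise.

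**The concern.** The protocol asks sites to record, and in part to re-grade, events carried over from the feeder study. Severity is an explicit part of the endpoint. Yet every specific output in SAP 6.6 that uses grade, seriousness (other than death) or discontinuation requires onset or worsening after the first study intervention. This goes beyond missing detail: an analyst who follows the stated rule will leave such events out of those outputs.

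The participants concerned are not off drug. Footnote a of the Schedule of Activities places them on feeder-study treatment during screening, so an SAE between consent and first rollover dose is an on-regorafenib event. Reporting elsewhere is not assured, because protocol section 9 makes pooling with feeder data optional. At stake is the completeness of the study report on its own safety endpoint, chiefly for non-fatal SAEs. No inference is at stake.

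**Working it through.** The plan has no figure to reproduce: protocol 9.1 plans no confirmatory test and 9.2 no sample size calculation. The check sets what must be recorded against what SAP 6.6 outputs.

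**Step 1: what the protocol makes reportable.** The Schedule of Activities has four recording items, three for AEs and one for SAEs.

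- (a) AEs leading to dose reduction, interruption or delay, or discontinuation: no onset condition; collected from consent (8.3.1).
- (b) Ongoing Grade 3/4 or vital-organ Grade 2 AEs, re-graded: onset before entry.
- (c) New Grade 3/4 or vital-organ Grade 2 AEs: collected from consent (8.3.1).
- (d) Ongoing or new SAEs: collected from consent (8.3.1).

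Items that begin only at the first rollover dose: 0 of 4. Items that name ongoing events: 2 of 4 (b and d).

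**Step 2: what SAP 6.6 outputs.**

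- Categories: TEAEs, drug-related TEAEs, TEAEs leading to discontinuation, TESAEs, drug-related TESAEs, TESAEs leading to discontinuation. Treatment-emergent only: 6 of 6.
- Listing items: TESAEs and TEAEs leading to discontinuation are restricted (2 of 4); deaths and pregnancies are not (2 of 4).

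**Step 3: match the two, for participants in the Safety set.**

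| Reportable event | Grade output | SAE listing | Discontinuation category and listing |
|---|---|---|---|
| Starts or worsens after first rollover dose | Yes | Yes, if serious | Yes |
| Ongoing Grade 3/4 or vital-organ Grade 2 AE, re-graded, not worsening | None named | Not applicable if non-serious | None named |
| Ongoing SAE, not worsening | None named | None named, unless fatal | None named |
| Starts or worsens between consent and first rollover dose, not later | None named | None named, unless fatal | None named |

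The last three rows lie inside the endpoint and inside the Safety set.

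**Step 4: look for cover elsewhere.**

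- SAP 4.1 promises descriptive analysis of all variables and frequency tables for categorical ones. Protocol section 9 likewise promises summary statistics, frequencies or listings. Both are firm, but neither names an AE output.
- SAP 4.2 says only "All data available will be analyzed".
- SAP 4.3 reports "The number of subjects who prematurely discontinue the study and study treatment for any reason", together with the reasons. A treatment-ending carried-over event therefore still shows in disposition, but not by event term, grade or relatedness.
- SAP 4.5 says "Otherwise valuable data which is not available in the safety set will also be analysed". That concerns data outside the Safety set, whereas the events here are inside it.
- Protocol 9.4 mentions AE listings, including serious AEs, only as something that may be provided.

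None of these commits to showing the last three rows by grade or seriousness.

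**The case against.** The strongest reply is that this is ordinary practice. Collecting from consent and tabulating from first dose is a usual pairing, protocol 9.4.2 delegates details to the SAP, and the SAP adds an unfiltered AE overview. CTCAE grade and seriousness are categorical data, so SAP 4.1 could be read as covering them. SAP 4.3 also presupposes a subject listing at CRF level.

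The affected set should also be very small. Inclusion criteria 3 and 4 and exclusion criterion 1 keep out participants who are not fit for a further cycle. Consent is signed at the feeder end-of-treatment visit and a seamless transition is expected, with any interruption held to 28 days including the week off. The window before the first rollover dose should therefore be short. Undated events default to treatment-emergent. SAEs reach the sponsor within 24 hours in any case, so safety oversight does not depend on these tables.

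Most of this stands, and it sets the size of the point. It does not close the gap. Delegation makes the SAP the place to specify the output, the overview has no stated content, and the general promises sit beside a specific section that filters these events out.

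Two stronger readings should be resisted. A reader might infer that non-emergent events go wholly unreported. The documents do not support that: the overview is unfiltered, deaths and pregnancies are listed without restriction, discontinuation reasons are reported, and SAP 4.1 promises general frequency output. A reader might also infer that the safety results are biased or the treatment-emergent filter wrong. That is not supported either: new and worsened events are fully tabulated, which suits an incidence analysis, and the documents give no count from which to claim a shift.

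**Conclusion.** The point holds as a minor mismatch between endpoint and analysis. For dosed participants, SAP 6.6 names no specific grade output, non-fatal SAE listing or AE-discontinuation category for reportable events that neither start nor worsen after the first rollover dose, although the primary safety endpoint includes them. The counts above describe scope, not effect: the number of affected events cannot be derived from the documents, is probably small and may be zero.

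The conclusion assumes that the first study intervention in SAP 6.6 means the first rollover dose. The synopsis, which starts the treatment period at that dose, and the Safety set definition both support this. If the first feeder dose were meant, most ongoing feeder events would count as treatment-emergent and the gap would shrink, but the SAP does not say so. Participants who consent but take no rollover dose are outside this point.

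**What to change.** In SAP 6.6:

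1. Keep the TEAE tables by SOC, PT and CTCAE grade unchanged as the incidence analysis.
2. Add one subject listing, in the Safety set, of all SAEs and protocol-specified AEs recorded from consent to the safety follow-up. Show the CTCAE v5.0 grade and a three-level flag: treatment-emergent; started or worsened between consent and first rollover dose; ongoing at entry without worsening. The flag keeps carried-over events apart from new ones.
3. Count AEs leading to discontinuation of study drug by the action taken in this study, regardless of onset date.

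With few patients expected, a listing is enough and a further table is not needed. The cost is SAP wording, one extra listing from data the protocol already requires, and possibly a small change in the discontinuation count. No protocol amendment or new data collection is needed.

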1.3 Schedule of Activities (SoA)

Table 1-1: Schedule of activities

Procedure	Screening ^a	Intervention Period ^b [Cycles consisting of 4 weeks]		End of study treatment (up to 14 days after last dose)	Safety Follow-up (30-35 days after last dose, phone call)	Notes
		Cycle 1 Day 1 ^c	Cycle 4 Day 1 + every 3 months (+/- 1 week)			
Informed consent	X					
Inclusion and exclusion criteria	X					Including pregnancy test done by treating physician.
Demography	X					
Tumor type	X					
Medical history	X					Medical important events, e.g. Grade 3/4 (S)AEs, since the start of treatment in the feeder study should be reported as medical history in this rollover study.
Study treatment		→→→→→→→→				Recheck clinical status before 1st dose of study medication. Regorafenib dosing as per feeder study protocol.
Drug dispensing		X	X			
Drug accountability		X	X	X		
AE review	X	X	X	X	X	To be documented only: 
 • AEs leading to dose reduction, interruption/delay and discontinuation • Any ongoing Grade 3 and 4 AEs, or Grade 2 AEs that affect vital organs (e.g. heart, liver) per feeder study protocol CTCAE version. These events need to be regraded by the investigator

						according to CTCAE Ver 5.0. • Any new CTCAE Ver 5.0 Grade 3 and 4 AEs, or Grade 2 AEs that affect vital organs (e.g. heart, liver)
SAE review	X	X	X	X	X	To be documented any ongoing or new SAEs
Concomitant medication review	X	X	X	X	X	

Abbreviations: AE - adverse event; CTCAE - Common terminology criteria for adverse events; SAE - serious adverse event.

a During the screening period the participant will be on treatment under the umbrella of the feeder study. At the end of treatment visit of the feeder study, eligibility criteria will be reviewed and the participants should sign informed consent for the rollover study.

b Safety assessments should be done according to local standard of care and regorafenib label information by the treating physician.

c The treating investigator should ensure a seamless transition without a change in the treatment schedule. Any treatment interruption should not exceed 28 consecutive days including 1 week break.

2. Introduction

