2.3 Benefit/Risk Assessment

Only participants who have been treated in a previous Bayer-sponsored regorafenib study and are still benefiting from treatment will be allowed to be enrolled in this study. They will continue treatment on the dose level that has been well tolerated before.

The site's principal investigator of the regorafenib study to which the subject is initially assigned, is expected to assess the overall benefit/risk for each participant. When the investigator deems there is a positive benefit/risk assessment the participant can be included in this rollover study.

More detailed information about the known and expected benefits and risks and reasonably expected adverse events of regorafenib may be found in the Investigator's Brochure (IB).

3. Objectives and Endpoints

Objectives	Endpoints
Primary	

 • The primary purpose of the program is to enable participants, currently receiving regorafenib in a Bayer sponsored clinical trial and assessed by the PI to be benefitting, to continue regorafenib treatment after their respective study has met its primary completion date, or main data analysis, or has been stopped prematurely. • And the documentation of safety 	
 • Frequency and severity of SAEs and protocol-specified AEs
Secondary	

 • Documentation of tolerability 	
 • Frequency of dose modifications

4. Study Design

This is an open-label study that will enable participants currently receiving regorafenib in a completed Bayer-sponsored regorafenib clinical trial to continue treatment. A completed study is defined as one that has reached the primary completion endpoint, main data analysis, or has been stopped prematurely, and the respective data have been cleaned.

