9.4.2 Safety Analyses

All safety analyses will be performed on the Safety analysis set.

Serious adverse events and protocol-specified AEs will be analyzed descriptively by providing frequency tables of SAEs and AEs observed during the study.

Tolerability of the study drug will be evaluated by displaying the number of dose modifications in frequency tables.

Details will be given in the statistical analysis plan.

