10.3.3 Recording and Follow-Up of AE and/or SAE**AE and SAE Recording**

- When an AE/SAE occurs, it is the responsibility of the investigator to review all documentation (eg, hospital progress notes, laboratory reports, and diagnostics reports) related to the event.
- The investigator will then record all relevant AE (those AEs leading to dose reduction, interruption/delay and discontinuation and any new Any new CTCAE version 5.0 Grade 3 and 4 AEs, or Grade 2 AEs that affect vital organs [e.g. heart, liver]) and all SAE information in the CRF.
- It is **not** acceptable for the investigator to send photocopies of the participant's medical records to the medical monitor or Bayer's pharmacovigilance department in

lieu of completion of the completed/AE/SAE CRF page.

- There may be instances when copies of medical records for certain cases are requested by the medical monitor or Bayer's pharmacovigilance department. In this case, all participant identifiers, with the exception of the participant number, will be redacted on the copies of the medical records before submission to the medical monitor or Bayer's pharmacovigilance department.
- The investigator will attempt to establish a diagnosis of the event based on signs, symptoms, and/or other clinical information. Whenever possible, the diagnosis (not the individual signs/symptoms) will be documented as the AE/SAE.

Assessment of Intensity

The investigator will make an assessment of intensity for each AE and SAE reported during the study and assign it as per CTCAE Ver 5.0.

Assessment of Causality

- The investigator is obligated to assess the relationship between study intervention and each occurrence of each AE/SAE.
- A "reasonable possibility" of a relationship conveys that there are facts, evidence, and/or arguments to suggest a causal relationship, rather than a relationship cannot be ruled out.
- The investigator will use clinical judgment to determine the relationship.
- Alternative causes, such as underlying disease(s), concomitant therapy, and other risk factors, as well as the temporal relationship of the event to study intervention administration will be considered and investigated.
- The investigator will also consult the Investigator's Brochure (IB) and/or Product Information, for marketed products, in his/her assessment.
- For each AE/SAE, the investigator **must** document in the medical notes that he/she has reviewed the AE/SAE and has provided an assessment of causality.

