6.3 Study drug exposure

Study drug exposure will be analyzed in the safety set.

Treatment duration will be summarized as well as the number of applications and modifications of the study drug.

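### Does SAP 6.6 need separate outputs for adverse events that led to dose reduction or interruption, and a label saying that collection was selective?

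*SAP*

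**What the plan says.** The protocol collects adverse events selectively. The adverse-event row of the Schedule of Activities (Section 1.3) opens with "To be documented only" and its first item is "AEs leading to dose reduction, interruption/delay and discontinuation". The other items are Grade 3 and 4 events, and Grade 2 events affecting vital organs. Serious events are all recorded, in a separate row. Section 10.3.3 repeats the rule: "The investigator will then record all relevant AE (those AEs leading to dose reduction, interruption/delay and discontinuation".

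The primary safety endpoint in Protocol Section 3 is "Frequency and severity of SAEs and protocol-specified AEs", and the tolerability endpoint is the frequency of dose modifications. Section 9.4.2 describes the safety analysis: "Serious adverse events and protocol-specified AEs will be analyzed descriptively by providing frequency tables of SAEs and AEs observed during the study". It asks for dose-modification counts in frequency tables and leaves the detail to the SAP.

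SAP 6.6 tabulates treatment-emergent events: "The total number of patients experiencing TEAEs will be presented and tabulated by SOC and PT and CTCAE grade". It gives six categories: all, drug-related, and leading to discontinuation, each for treatment-emergent events and again for serious ones. For listings it says: "All deaths, TESAEs, TEAEs leading to discontinuation and pregnancies will be presented in subject listings, if applicable". SAP 6.3 covers dosing: "Treatment duration will be summarized as well as the number of applications and modifications of the study drug".

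**The concern.** There are two strands.

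First, the protocol names three kinds of dose action that make an event reportable, and the SAP gives an output to only one of them. A non-serious event that led to a reduction or an interruption is counted among all treatment-emergent events, but nothing marks it as having changed the dose. SAP 6.3 counts modifications without cause or direction. That count could include re-escalations, which Protocol 6.6 allows, and interruptions around surgery, which Protocol 6.5.2 foresees. The report would then show how often doses changed and which events ended treatment, but not which events led to reductions or interruptions.

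Second, the SAP calls its tables treatment-emergent adverse events by grade and does not say that low-grade events were mostly not sought. A reader could take the Grade 1 and Grade 2 counts as full incidence.

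**Working it through.** No sample size, error rate or event target is involved, so the check is a comparison of texts.

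**1. Endpoint against output.**

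| Protocol Sections 3 and 9.4.2 | SAP output | Delivered? |
|---|---|---|
| Frequency and severity of serious and protocol-specified events | 6.6: tables by system organ class, preferred term and CTCAE grade, with serious events as their own category | Yes |
| Frequency of dose modifications | 6.3: number of modifications | Yes |
| Events cross-classified by reduction or interruption | None | Not asked for |

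**2. Dose-action classes against SAP 6.6.**

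- Categories: 6. Concerning action taken: 2, both discontinuation. Concerning reduction or interruption/delay: 0.
- Listings: 4 (deaths, serious events, events leading to discontinuation, pregnancies). Defined by discontinuation: 1. Defined by reduction or interruption/delay: 0.
- Dose-action classes in the protocol: 3. With an output of their own: 1 of 3.

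The textual gap is therefore real.

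**3. What happens to an affected event.** Take a new, non-serious Grade 2 hand-foot skin reaction during the rollover study. Protocol Table 6-3 links its first occurrence to a dose decrease, so the Schedule of Activities requires it to be recorded. It enters the SAP 6.6 table under its term and grade, and the drug-related category if judged related. The dose change enters the SAP 6.3 count. Both facts are reported; the link between them is not. Had the event been serious, it would also appear in the listing of serious events. What is lost is thus one attribute of non-serious events, not the events themselves.

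**4. Can the size of the lost link be bounded?** If interruptions count as modifications, the number of patients with an event leading to reduction or interruption cannot exceed the smaller of (a) patients with any modification and (b) patients with any treatment-emergent event. SAP 6.6 reports (b). The documents give neither number, nor a total enrolled, so no figure follows.

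**5. What selective collection does by grade.**

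| Grade | Recorded under the Schedule of Activities |
|---|---|
| 1 | Only if serious or leading to a dose action |
| 2 | As Grade 1, plus events affecting vital organs |
| 3 and 4 | All |
| Fatal | Through serious-event reporting |

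Protocol 8.3.1 and 8.4 ask for some further events without a grade limit, which does not make low-grade collection complete. The low-grade cells are incomplete by design. The serious and Grade 3 to 4 counts are not understated. Since essentially only serious and protocol-specified events are recorded, a table of what was recorded is in substance the endpoint in Section 3, whatever its title.

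**The case for a change.** The strongest case for a change runs as follows. Tolerability is the secondary objective. Protocol Tables 6-2 to 6-5 manage toxicity largely through reduction and interruption, and Section 7.1 ends treatment when more than two reductions are needed. Knowing which toxicities drove those actions is the natural tolerability question, and sites already record the events. Section 9.4.2 hands the detail to the SAP, so the SAP is the place for it. Small numbers justify dropping subgroups, but a listing is cheap and most useful when patients are few. On the label, Grade 2 rows will differ between terms because of the recording rule: Table 6-2 leaves the dose unchanged for a Grade 2 toxicity, while Table 6-3 reduces it for hand-foot skin reaction. Protocol Section 9 also allows pooling with feeder-study data.

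Part of this stands. The display would be informative, and a footnote on the recording rule would be good practice. The rest does not carry. Naming an event type as a reason to record it does not promise a separate table, and the tolerability endpoint is written as a count of modifications. SAP Section 7 says the analyses were updated because few patients entered, and Section 6 plans nothing beyond summary statistics, so a short output set is deliberate. Protocol 9.4 already permits further descriptive listings of adverse events and dose modifications where appropriate. The pooling point rests on a permissive sentence, on no pooled table in this SAP, and on an assumption about how feeder studies collected events that the documents do not settle.

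**Conclusion.** The observation is accurate, but it does not call for a change. SAP 6.6 gives no output of its own to 2 of the 3 dose-action classes and does not state that its tables hold selectively collected events. Both protocol endpoints are nevertheless delivered as written, no required analysis is missing, and no endpoint estimate is biased. Protocol 9.1 plans no hypothesis test, so no conclusion depends on the missing cross-classification. This is a gap in presentation that an analyst can fill when building the tables, by flagging the dose action in the event display and noting the recording rule beneath it.

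Two conditions apply. The case report form is not among the documents, so whether its action-taken field separates reduction from interruption is unknown. The view on labelling assumes that readers take the tables together with the protocol, which the SAP references. The number of events affected cannot be stated, because the documents give no patient or event counts.

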1.1 Synopsis

Protocol Title: A single arm, open-label, multicenter Phase 2 study of regorafenib in participants who have been treated in a previous Bayer-sponsored regorafenib study (monotherapy or combination treatment) that has reached the primary completion endpoint, or main data analysis, or has been stopped prematurely.

Short Title: Regorafenib rollover study

Rationale: The primary purpose of the study is to enable participants, currently receiving regorafenib in a Bayer-sponsored clinical trial, to continue treatment after their respective study has reached the primary completion endpoint, main data analysis, or has been stopped prematurely, and the respective data have been cleaned. Participants will be able to continue treatment until the treating physician feels the participant is no longer benefiting from treatment.

Objectives

Objectives	
Primary	
The primary purpose of the program is to enable participants, currently receiving regorafenib in a Bayer-sponsored clinical trial and assessed by the principal investigator (PI) to be benefitting, to continue regorafenib treatment after their respective study has reached the primary completion endpoint, or main data analysis, or has been stopped prematurely.And the documentation of safety
Secondary	
Documentation of tolerability

Overall Design:

This is an open-label study that will enable participants currently receiving regorafenib in a completed Bayer-sponsored regorafenib clinical trial to continue treatment. A completed study is defined as one that has reached the primary completion endpoint, or main data analysis, or has been stopped prematurely, and the respective data have been cleaned.

Disclosure Statement: This is an open-label study that will enable participants currently receiving regorafenib in a completed Bayer-sponsored regorafenib clinical trial to continue treatment.

Number of Participants:

Participants who are currently receiving treatment in on-going regorafenib studies may be eligible to enroll in the study. There may be periods when there are no active participants in this study but it will remain open for enrollment.

Intervention Groups and Duration:

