2.1 Study Rationale

The primary purpose of the study is to enable participants, currently receiving regorafenib in a Bayer sponsored clinical trial, to continue treatment after their respective study has been completed. A completed study is defined as one that has reached the primary completion endpoint, main data analysis, or has been stopped prematurely, and the respective data have been cleaned. Participants will be able to continue treatment until the treating physician feels the participant is no longer benefiting from treatment.

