>20 times ULN	Any occurrence	Discontinue treatment with regorafenib permanently.
>3 times ULN with concurrent bilirubin >2 times ULN	Any occurrence	Discontinue treatment with regorafenib permanently. Monitor liver function weekly until resolution or return to baseline. Exception: patients with Gilbert's syndrome who develop elevated transaminases should be managed as per the above outlined recommendations for the respective observed elevation of ALT and / or AST.

Abbreviations: ALT – alanine transaminase; AST – aspartate transaminase; ULN = upper limit of normal.

If a dose reduction has been performed within this study protocol intra subject dose reescalation can be considered up to the starting dose in this rollover study protocol at the discretion of the treating physician.

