8.3.1 Time Period and Frequency for Collecting AE and SAE Information

All SAEs will be collected from the signing of the informed consent form (ICF until the safety follow-up visit (Section 1.3).

AEs, as described in the SoA, (ie, AEs leading to dose reduction, interruption/delay and discontinuation and any new CTCAE Ver 5.0 Grade 3 and 4 AEs, or Grade 2 AEs that affect vital organs (e.g. heart, liver) will be collected from the signing of the ICF until the safety follow up- visit

Any ongoing Grade 3 and 4 AEs, or Grade 2 AEs that affect vital organs (e.g. heart, liver) per feeder study protocol CTCAE version need to be reported as AEs in this rollover study. These events need to be re-graded by the investigator according to CTCAE Ver 5.0.

Medical important events, e.g. Grade 3/4 (S)AEs, since the start of treatment in the feeder study should be reported as medical history in this rollover study.

Medical occurrences that begin before the start of study intervention but after obtaining informed consent will be recorded on the AE section of the case report form (CRF).

Medical occurrences that started before but deteriorated after obtaining informed consent will be recorded as adverse events.

All SAEs will be recorded and reported to the sponsor or designee immediately and under no circumstance should this exceed 24 hours, as indicated in Appendix 3 (Section 10.3). The investigator will submit any updated SAE data to the sponsor within 24 hours of it being available.

Investigators are not obligated to actively seek AE or SAE after conclusion of the study participation. However, if the investigator learns of any SAE, including a death, at any time after a participant has been discharged from the study, and he/she considers the event to be reasonably related to the study intervention or study participation, the investigator must promptly notify the sponsor.

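### Do the crude AE and dose-modification counts need a time-on-drug adjustment because treatment length is open-ended?

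*SAP*

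**What the plan says.** Treatment is open-ended. Protocol 2.1 states: "Participants will be able to continue treatment until the treating physician feels the participant is no longer benefiting from treatment". The Synopsis (Protocol 1.1) adds: "There may be periods when there are no active participants in this study but it will remain open for enrollment". Under Protocol 8.3.1 the selected AEs "will be collected from the signing of the ICF until the safety follow"-up contact, which the Schedule of Activities places 30 to 35 days after the last dose. The observation window therefore lengthens with time on drug.

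The endpoint table in Protocol Section 3 defines the primary safety endpoint as "Frequency and severity of SAEs and protocol-specified AEs" and the secondary endpoint as how often the dose is modified. For the latter, Protocol 9.4.2 says: "Tolerability of the study drug will be evaluated by displaying the number of dose modifications in frequency tables".

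SAP 6.6 plans the AE tables: "The total number of patients experiencing TEAEs will be presented and tabulated by SOC and PT and CTCAE grade". It also commits to subject listings of deaths, serious treatment-emergent events, treatment-emergent events leading to discontinuation, and pregnancies. SAP 6.3, also in the safety set, says: "Treatment duration will be summarized as well as the number of applications and modifications of the study drug". SAP 4.1 specifies what a summary of a metric variable contains: available and missing counts, mean, standard deviation, median, quartiles and range. SAP Section 6 plans nothing beyond summary statistics.

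**The concern.** When participants stay on drug for very different lengths of time, the percentage with at least one event mixes two things: how often events occur and how long people were watched. The same percentage can come from a high rate over a few months or a low rate over several years. The plan contains no patient-years at risk, rate per patient-year or per cycle, or cumulative incidence. Comparing these percentages directly with feeder-study figures of different exposure length would mislead.

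The dose-modification count raises a second doubt. Protocol 6.6 says that, after a reduction, "intra subject dose reescalation can be considered up to the starting dose in this rollover study protocol". Neither document defines which changes count as modifications, so one total might combine reductions and interruptions with increases. At stake is how the two reported endpoints are read; no test or decision rule is involved.

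**Working it through.** The documents give no event rate, exposure or expected number of participants, so there is no planned figure to reproduce. All rates, durations and numbers of participants below are assumptions.

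**Step 1. How far the crude percentage depends on time.** With a constant first-event rate r per patient-year and follow-up of t years, the crude percentage is 100 × (1 − exp(−r t)).

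| r | t = 0.25 | t = 1 | t = 3 |
|---|---|---|---|
| 0.25 | 6.1% | 22.1% | 52.8% |
| 0.5 | 11.8% | 39.3% | 77.7% |
| 1.0 | 22.1% | 63.2% | 95.0% |

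If events come early (Weibull, 100 × (1 − exp(−0.5 × t^0.5))), the dependence is weaker: 22.1%, 39.3% and 57.9%.

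In reverse, a crude 40% implies a rate of −ln(0.6) / ((m + 1)/12) after m months on drug plus about one month of follow-up. That is 1.53 per patient-year at 3 months and 0.10 at 60 months, about a 15-fold range. Taken alone, the percentage is ambiguous.

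**Step 2. Whether the planned output leaves it alone.** It does not. The duration summary in SAP 6.3 gives total exposure as number of participants × mean duration. Suppose 5 of 10 participants have an event.

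- Mean duration 0.5 years: 10 × 0.5 = 5 patient-years, and 5/5 = 100 patients with an event per 100 patient-years of exposure.
- Mean duration 2 years: 10 × 2 = 20 patient-years, and 5/20 = 25 per 100 patient-years.

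Both give a crude 50%, but the planned duration table separates them at once: the mean is 6 months in one case and 24 months in the other.

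Dose modifications need even less, because a count of all modifications is not cut off at the first one. Ten modifications in 20 participants with a mean of 12 months give 10 / (20 × 1) = 0.5 per patient-year. With a mean of 24 months they give 10 / (20 × 2) = 0.25.

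**Step 3. What is still missing.** A first-event rate stops each affected participant's clock at the event, and the planned tables do not supply that time. The gap can be bounded if all 10 participants have the same duration and the post-treatment follow-up is ignored. Time at risk is lowest if all five events fall at first dose (only the five unaffected participants contribute) and highest if they fall at the end of treatment.

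- 0.5 years each: time at risk between 5 × 0.5 = 2.5 and 10 × 0.5 = 5 patient-years, so 5/2.5 = 200 down to 5/5 = 100 per 100 patient-years.
- 2 years each: between 5 × 2 = 10 and 10 × 2 = 20 patient-years, so 5/10 = 50 down to 5/20 = 25 per 100 patient-years.

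The derived rate is thus low by a factor of at most 2 here. The exact Poisson 95% intervals around it are 32.5 to 233.4 for 100, and 8.1 to 58.3 for 25. Even the extreme values of 200 and 50 lie inside. With unequal durations linked to events the gap could be larger, but at this size sampling error is already wide.

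**The case for a change.** The strongest reply is that duration and events are linked. Toxicity can end treatment (Protocol 4.1 and 7.1), so a separate duration summary cannot recover time to first event. The listings promised in SAP 6.6 leave out dose modifications and non-serious events that do not stop treatment, while Protocol 9.4 only allows such listings where appropriate. Results will be posted on public registries (Protocol 10.1.5), may be pooled with feeder data (Protocol Section 9) and may feed into feeder publications (Protocol 10.1.9). Adding patient-years would take two or three SAP sentences and dates already collected.

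Some of this stands. Time at risk to first event is not recoverable from the planned tables, the listing commitment is partial, and the meaning of a modification is unwritten.

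It does not make the plan wrong. No feeder comparison is committed to, and a rollover rate would not make one fair: participants enter because they benefit from the drug and are fit for another cycle, earlier exposure lies outside the clock, and only selected AEs are recorded. A single rate also assumes a roughly constant hazard and would be imprecise with few participants. A first-event rate would need restricting to treatment-emergent events, because feeder-study AEs still ongoing at entry are also reported here under Protocol 8.3.1. Deciding which changes count as modifications is a routine matter for the table specification.

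**Conclusion.** The observation is correct: treatment length is open-ended, and both endpoints are planned as counts with no exposure-based rate. No change to the plan is needed. Frequency tables estimate what Protocol Section 3 defines. The crude percentage validly describes the share of participants with an event during rollover treatment, and there is no hypothesis test or comparison between arms to distort. The planned duration summary shows whether exposure was months or years and yields total patient-years, patients with an event per patient-year of exposure, and modifications per patient-year. Serious events and events leading to discontinuation are listed by participant in any case.

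What remains is the absence of time to first event. In the illustrative 5-of-10 case this is worth at most a factor of 2, assuming equal durations and no post-treatment follow-up time. The plan was also revised in the light of the small number entering (SAP Section 7), so keeping it simple is a fair trade-off. An analyst who shows total patient-years beside the AE tables, or treatment duration and onset day in the listings, adds useful context but repairs no invalid result.
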